### Events that Do Not Meet the Definition of an SAE

Elective hospitalizations to administer, or to simplify trial treatment or trial procedures are not considered SAEs. However, all events leading to unplanned hospitalizations or unplanned prolongation of an elective hospitalization (for example, undesirable effects of any administered treatment) must be documented and reported as SAEs.

### Events Not to Be Considered as AEs/SAEs

Medical conditions present at the initial trial visit that do not worsen in severity or frequency during the trial are defined as Baseline Medical Conditions, and are not to be considered AEs.

### Adverse Events of Special Interest

The following is considered pre-defined AESIs for this trial:

Hypersensitivity (defined by Standardized MedDRA Query [SMQ] narrow as per the latest MedDRA version).

## 7.4.2.2 Methods of Recording and Assessing Adverse Events

At each trial visit, the patient will be queried on changes in his or her condition. During the reporting period, any unfavorable changes in the patient's condition will be recorded as AEs, whether reported by the patient or observed by the Investigator.

Complete, accurate, and consistent data on all AEs experienced for the duration of the reporting period (defined below) will be reported on an ongoing basis in the appropriate section of the CRF. All SAEs must be additionally documented and reported using the appropriate SAE Report Form as described in Section [7.4.2.4](#).

It is important that each AE report include a description of the event, its duration (onset and resolution dates and times when it is important to assess the time of AE onset relative to the

recorded treatment administration time), its severity, its causal relationship with the trial treatment, any other potential causal factors, any treatment given or other action taken, including dose modification or discontinuation of the IMP, and its outcome. In addition, serious cases should be identified and the appropriate seriousness criteria documented.

Specific guidance can be found in the CRF Completion and Monitoring Conventions provided by the Sponsor.

#### **7.4.2.3                   Definition of the Adverse Event Reporting Period**

The AE reporting period for safety surveillance begins when the patient is initially included in the trial (date of first signature of informed consent/date of first signature of first informed consent) and continues until the 4-month safety follow-up/end of trial visit.

Any SAE assessed as related to IMP and all AESIs must be reported whenever it occurs, irrespective of the time elapsed since the last administration of IMP.

#### **7.4.2.4                   Procedure for Reporting Serious Adverse Events, Adverse Events of Special Interest and Dose Limiting Toxicities**

##### **Serious Adverse Events**

In the event of any new SAE occurring during the reporting period, the Investigator must immediately (within a maximum of 24 HOURS after becoming aware of the event) inform the Sponsor or its designee using the SAE Report Form following specific completion instructions.

In exceptional circumstances, an SAE (or follow-up information) may be reported by telephone; in these cases, an SAE Report Form must be provided immediately thereafter.

Relevant pages from the CRF may be provided in parallel (for example, medical history, concomitant drugs). Additional documents may be provided by the Investigator, if available (for example, laboratory results, hospital report, autopsy report). In all cases, the information provided on the SAE Report Form must be consistent with the data about the event recorded in the CRF.

The Investigator must respond to any request for follow-up information (for example, additional information, outcome, final evaluation, other records where needed) or to any question the Sponsor/designee may have on the AE within the same timelines as those noted above for initial reports. This is necessary to ensure prompt assessment of the event by the Sponsor or designee and (as applicable) to allow the Sponsor to meet strict regulatory timelines associated with expedited safety reporting obligations.

Requests for follow-up will usually be made via the responsible Monitor, although in exceptional circumstances the Global Drug Safety department may contact the Investigator directly to obtain further information or to discuss the event.

## Adverse Events of Special Interest

The AESIs have to be reported in an expedited manner (like the SAEs outlined above) using the AESI form.

### 7.4.2.5 Safety Reporting to Health Authorities, Independent Ethics Committees/ Institutional Review Boards and Investigators

The Sponsor will send appropriate safety notifications to Health Authorities in accordance with applicable laws and regulations.

The Investigator must comply with any applicable site-specific requirements related to the reporting of SAEs (particularly deaths) involving trial patients to the IEC/IRB that approved the trial.

In accordance with ICH GCP, the Sponsor/designee will inform the Investigator of “findings that could adversely affect the safety of patients, impact the conduct of the trial or alter the IEC’s/IRB’s approval/favorable opinion to continue the trial.” In particular and in line with respective regulations, the Sponsor/designee will inform the Investigator of AEs that are both serious and unexpected and are considered to be related to the administered product (“suspected unexpected serious adverse reactions” or SUSARs). The Investigator should place copies of Safety Reports in the Investigator Site File. National regulations with regard to Safety Report notifications to Investigators will be taken into account.

When specifically required by regulations and guidelines, the Sponsor/designee will provide appropriate Safety Reports directly to the concerned lead IEC/IRB and will maintain records of these notifications. When direct reporting is not clearly defined by national or site-specific regulations, the Investigator will be responsible for promptly notifying the concerned IEC/IRB of any Safety Reports provided by the Sponsor/designee and of filing copies of all related correspondence in the Investigator Site File.

For trials covered by the European Directive 2001/20/EC, the Sponsor’s responsibilities regarding the reporting of SAEs/SUSARs/Safety Issues will be carried out in accordance with that Directive and with the related Detailed Guidance documents.

### 7.4.2.6 Monitoring of Patients with Adverse Events

AEs are recorded and assessed continuously throughout the trial (see Section 7.4.2.3) and are assessed for final outcome at the 4-month safety follow-up visit. All SAEs ongoing at the 4-month safety follow-up visit must be monitored and followed up by the Investigator until stabilization or until the outcome is known, unless the patient is documented as “lost to follow-up.” Reasonable attempts to obtain this information must be made and documented. It is also the responsibility of the Investigator to ensure that any necessary additional therapeutic measures and follow-up procedures are performed.

#### 7.4.3

#### Pregnancy and In Utero Drug Exposure

Only pregnancies considered by the Investigator to be related to trial treatment (for example, resulting from a drug interaction with a contraceptive medication) are considered to be AEs. However, all pregnancies with an estimated conception date during the period defined in Section 7.4.2.4 must be recorded by convention in the AE page/section of the CRF. The same rule applies to pregnancies in female patients and to pregnancies in female partners of male patients. The Investigator must notify the Sponsor/designee in an expedited manner of any pregnancy using the Pregnancy Report Form, which must be transmitted according to the same process as described for SAE reporting in Section 7.4.2.4.

Investigators must actively follow up, document, and report on the outcome of all these pregnancies, even if the patients are withdrawn from the trial.

The Investigator must notify the Sponsor/designee of these outcomes using the paper Pregnancy Report Form. If an abnormal outcome occurs, the SAE Report Form will be used if the patient sustains an event and the Parent-Child/Fetus Adverse Event Report Form if the child/fetus sustains an event.

Any abnormal outcome must be reported in an expedited manner as described in Section 7.4.2.4, while normal outcomes must be reported within 45 days after delivery.

In the event of a pregnancy in a patient occurring during the course of the trial, the patient must be discontinued from IMP immediately. The Sponsor/designee must be notified without delay and the patient must be followed as mentioned above.

#### 7.4.4

#### Clinical Laboratory Assessments

Blood and urine samples will be collected for the following clinical laboratory tests, following the timing noted in the Schedule of Assessments (Table 1) and sent to the central laboratory for analysis. All samples should be clearly identified.

The Sponsor should receive a list of laboratory normal ranges before shipment of trial drug. Any change in laboratory normal ranges during the trial should be forwarded to the Sponsor or designee in a timely manner.

For women of childbearing potential, a qualitative serum pregnancy test will be performed at screening only, and an on-site urine test will be performed at baseline, Weeks 4, 8, 12, 24, 36, 48, and 52, the early termination visit, and the safety follow-up visits. The dipstick and urine pregnancy testing will be done locally only. If abnormal dipstick findings are observed, a urine sample will be sent to the central laboratory for microscopy. When there is no site visit, the female patients will perform urine pregnancy tests themselves at home, ie, at Weeks 16, 20, 28, 32, 36, 40, and 44. The patient should be instructed to immediately contact the Investigator if she identifies a positive urine pregnancy test result.

The ESR will be assessed locally only.

Local clinical laboratory samples may be collected for emergency safety evaluations but are not required to be collected/recorded in the CRFs.

The blood samples listed in [Table 3](#) will be drawn, processed, and stored in accordance with the directions provided in the Laboratory Manual (also see [Appendix C](#)).

**Table 3** Clinical Laboratory Assessments

Hematology	White blood cell count, red blood cell count, hemoglobin, hematocrit, mean corpuscular volume, mean corpuscular hemoglobin concentration, platelet count, erythrocyte sedimentation rate, neutrophils (absolute and percentage), lymphocytes (absolute and percentage), monocytes (absolute and percentage), eosinophils (absolute and percentage), basophils (absolute and percentage)
Biochemistry	Sodium, potassium, blood urea nitrogen, creatinine, alkaline phosphatase, alanine aminotransferase, aspartate aminotransferase, gamma-glutamyl transferase, lactate dehydrogenase, serum albumin, calcium, phosphate, glucose, creatine kinase, uric acid, total bilirubin, total serum protein, cholesterol, triglycerides, C-reactive protein, coagulation (activated partial thromboplastin time and prothrombin time)
Urinalysis	Dipstick, including macroscopic appearance, bilirubin, blood, color, glucose, ketones, leukocyte esterase, nitrite, pH, protein, specific gravity, and urobilinogen. Full urinalysis (dipstick plus microscopic evaluation) at the Investigator's discretion only if warranted by an abnormal dipstick finding.
Viral serology	Hepatitis B surface antigen, hepatitis B core antibody, hepatitis C antibody, HIV types 1 and 2
Other	Pregnancy test (women only), rheumatoid factor (RF), anti-citrullinated protein antibodies (ACPA), anti-nuclear antibody, anti-dsDNA, QuantiFERON Gold tuberculosis test

The following laboratory assessments will not be entered into the database: rheumatoid factor, pregnancy test, and viral serology.

#### 7.4.5 Vital Signs, Physical Examinations, and Other Assessments

Vital signs including body temperature, respiratory rate, and heart rate (after 5-minute rest) will be measured once at screening and throughout the trial at the visits indicated in the Schedule of Assessments. Arterial blood pressure (after 5-minute rest) will be measured twice using a validated device and recorded at the visits indicated in the Schedule of Assessments ([Table 1](#)).

A complete physical examination (including, eg, general appearance, skin, head/neck, pulmonary, cardiovascular, gastrointestinal, external genitourinary, lymphatic, musculoskeletal system, extremities, eyes [inspection and vision control], nose, throat, and neurologic status) will be performed at screening and at subsequent visits as documented in the Schedule of Assessments ([Table 1](#)) and the abnormal results documented in the CRF. All clinically significant abnormalities occurring before signature of informed consent should be recorded in the Medical History section and/or Disease History; all abnormalities occurring or worsening after signature of informed consent should be recorded in the Adverse Events section. Abnormal findings are to be reassessed at subsequent visits.

Body weight will be recorded at screening and at subsequent visits as indicated in the Schedule of Assessments ([Table 1](#)) and documented in the CRF. Height will be measured at screening only.

A 12-lead ECG and chest X-ray will be recorded as indicated in the Schedule of Assessments ([Table 1](#)).

All newly diagnosed or worsening conditions, signs, and symptoms observed from screening, whether related to trial treatment or not, are to be reported as AEs.

For women of childbearing potential, a serum  $\beta$ -hCG pregnancy test will be carried out during the screening phase only, and a urine pregnancy test will be performed at the on-site visits (baseline, Weeks 4, 8, 12, 24, 36, 48, and 52, the early termination visit and the safety follow-up visit) and at home (Weeks 16, 20, 28, 32, 36, 40, and 44) as indicated in the Schedule of Assessments ([Table 1](#)).

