15.1 Primary Endpoint Analyses

The primary endpoint is the occurrence of treatment-emergent AESIs (hypersensitivity) up to Week 52.

The primary analysis will be based on the safety analysis set.

The following is considered pre-defined AESI for this trial:

Hypersensitivity (defined by Standardized MedDRA Queries [SMQs] narrow as per the latest MedDRA version).

The proportions of subjects with AESIs (hypersensitivity) and accompanying 95% CIs (Exact 95% CIs, calculated with the Clopper-Pearson method) will be provided for each treatment arm. Half width of 95% CIs for the difference between treatment arms in occurrence for the most commonly observed clinical events of AESI (hypersensitivity) will also be presented. The cut-off point for the selection of the most commonly observed clinical events will be decided prior to the database lock and the treatment unblinding.

Listings of all AESIs (hypersensitivity) and listings of AESIs (hypersensitivity) with NCI-CTCAE Grade \geq 3 will be provided.

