16.1 Adverse Events

Adverse events will be collected throughout the study and coded using version 19.1 of MedDRA or later.

Treatment-emergent adverse events (TEAEs) are those events that start on or after the day of first administration of study treatment. If an AE started on the same date as the first administration of the first study treatment given, the timing related to study treatment as recorded on the adverse events page of the eCRF will be taken into account when determining treatment emergence. A worst case approach will be used, ie if time is missing or if the AE occurred at the same time as the first administration of the first study treatment given, then the AE will be classified as treatment-emergent.

Incomplete AE-related dates will be handled as follows:

- In case the onset date is missing completely or missing partially but the onset month and year, or the onset year are equal to the start of study treatment then the onset date will be replaced by the minimum of start of study treatment and AE resolution date.
- In all other cases the missing onset day or missing onset month will be replaced by 1.
- Incomplete stop dates will be replaced by the last day of the month (if day is missing only), if not resulting in a date later than the date of subject's death. In the latter case the date of death will be used to impute the incomplete stop date.
- In all other cases the incomplete stop date will not be imputed.

Only TEAEs will be included in tables and will be summarized by treatment arm. All AEs will be listed.

Unless otherwise stated, TEAEs will be displayed in terms of frequency tables: primary SOC in alphabetical order, then PT in order of decreasing frequency across both treatment arms. If a subject has more than one event for a particular SOC or PT, then the event will be counted once only for the subject. For example, if a subject has two different TEAEs but these are within the same SOC, then they will be counted once for each PT but only once for the SOC. If at any time a summary is being prepared on data that are not fully coded, uncoded TEAEs will be summarized with a SOC as 'Uncoded' and the PT term will be set to the TEAE verbatim text.

If an AE is reported for a given subject more than once during treatment, the worst relationship to study treatment will be tabulated.

Adverse events related to study treatment are those events with relationship missing, unknown or yes.

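### The SAP defines a treatment-emergent event by start date alone, so an event that opens in screening and worsens on drug goes uncounted if it is kept as one record

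*Protocol*

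**What the plan says.** The protocol treats worsening as an adverse event. Under 7.4.5, "All newly diagnosed or worsening conditions, signs, and symptoms observed from screening, whether related to trial treatment or not" must be reported as adverse events, and "all abnormalities occurring or worsening after signature of informed consent should be recorded in the Adverse Events section". The exemption in 7.4.2.1 covers only what does not worsen: "Medical conditions present at the initial trial visit that do not worsen in severity or frequency during the trial are defined as Baseline Medical Conditions". Collection starts before dosing (7.4.2.3): "The AE reporting period for safety surveillance begins when the patient is initially included in the trial", which the section ties to the date of consent. Screening runs from 28 to 3 days before the first dose (7.1.1).

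The protocol uses the term treatment-emergent but does not define it. The only definition is in SAP 16.1: "Treatment-emergent adverse events (TEAEs) are those events that start on or after the day of first administration of study treatment". The SAP adds rules for onsets on the day of first dose and for missing or partial onset dates, but none for worsening. It continues: "Only TEAEs will be included in tables and will be summarized by treatment arm". All adverse events are listed.

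The primary analysis inherits this filter (SAP 15.1): "The primary endpoint is the occurrence of treatment-emergent AESIs (hypersensitivity) up to Week 52".

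Protocol 7.4.2.2 asks each report for onset, resolution, severity and seriousness. It leaves further recording detail to CRF conventions that are not among the supplied documents.

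**The concern.** The two documents use different tests. The protocol asks whether a condition is new or worse; the SAP asks only when the record starts. Take a Grade 1 rash that begins in screening and becomes Grade 3 after dosing. If the site updates the existing record, its start date stays before the first dose. It then fails the SAP definition and is left out of the primary proportion, its confidence interval, the between-arm difference, and the serious and by-grade tables.

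Safety is the primary objective, and aggravation of an existing reaction is one way a difference between products could show. Screening onsets should balance between arms because they precede dosing. Worsening on drug happens after randomization and need not balance.

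The SAP also treats comparable data differently. Laboratory values and vital signs are tabulated as shifts from baseline to the worst on-treatment value (16.3, 16.4). Adverse events, which carry the primary endpoint, have no equivalent.

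**Working it through.** **Step 1. Follow each kind of record through the SAP rule.**

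| Situation | Onset date used | In AE tables, and in the primary proportion if an AESI? |
|---|---|---|
| Event starts after first dose | Actual date | Yes |
| Condition predates consent and worsens on drug | Date of worsening, because it is not an AE until then (Protocol 7.4.2.1, 7.4.5) | Yes, on the natural reading |
| AE starts in screening and worsens on drug; new record opened | Date of worsening | Yes |
| Same, kept as one record with a full onset date | Screening date | No; listing only |
| Same, one record, onset missing or partial and matching the month and year (or the year) of first dose | Earlier of first dose and resolution (SAP 16.1) | It can be |

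Only the fourth row is a loss. The last two rows are awkward side by side: a vague onset date can bring an event in, while an exact one keeps it out.

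**Step 2. The plan's own figure for the primary endpoint.** Protocol 8.1 gives a precision of 12.0% at an incidence of 26.0% (injection site reactions) and 9.0% at 11.0% (rash). The half-width of a 95% CI for a difference between two equal proportions is 1.96 × √(2p(1−p)/n). With n = 100 per arm:

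- p = 0.26: 1.96 × √(2 × 0.26 × 0.74/100) = 12.16 points
- p = 0.11: 1.96 × √(2 × 0.11 × 0.89/100) = 8.67 points

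Both agree with the plan to the whole point. This figure is not in dispute; it gives the scale for the rest.

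**Step 3. All adverse events.** The documents do not say how many patients fall in the fourth row, so this step rests on assumptions.

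- Protocol 5.2.3.3 cites a TEAE rate of up to 91% at Week 52. Assume a constant hazard that also applies in screening, which is generous because it is an on-treatment maximum: −ln(1 − 0.91)/52 = 0.0463 per week.
- Assume a screening period of 2 to 4 weeks: 1 − exp(−0.0463 × 2) = 8.8%; 1 − exp(−0.0463 × 4) = 16.9%.
- Assume 5% to 20% of these worsen after dosing, with no source in the documents, and that every one stays a single record.
- Low end: 0.088 × 0.05 × 260 = 1.1 patients. High end: 0.169 × 0.20 × 260 = 8.8 patients.

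That is about 1 to 9 patients, or 0.4% to 3.4% of 260.

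**Step 4. The primary endpoint.** A reaction at the study drug's injection site cannot precede the first injection, so the 26.0% component contributes nothing. For rash at 11.0%, by the same method:

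- Hazard: −ln(0.89)/52 = 0.00224 per week
- Screening onset: 0.45% over 2 weeks, 0.89% over 4 weeks
- Low end: 0.0045 × 0.05 × 260 = 0.06 patients. High end: 0.0089 × 0.20 × 260 = 0.46 patients, both arms together.

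The hypersensitivity query is wider than rash. Doubling the rate to 22%, again an assumption, gives at most about 1 patient: hazard −ln(0.78)/52 = 0.00478 per week; 1.89% over 4 weeks; 0.0189 × 0.20 × 260 = 0.98. One patient in an arm of 130 is 1/130 = 0.77 points, against the half-widths of 8.67 to 12.16 points in Step 2. A patient with any other treatment-emergent AESI is counted regardless.

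**The case against.** The strongest reply is that Protocol 7.4.5 makes the worsening itself the reportable event. Read that way, a worsening after first dose is an adverse event that starts after first dose and meets the SAP definition. SAP 16.1 also foresees an event being reported more than once for a patient, and Protocol 7.4.2.2 does not forbid a second record. The CRF conventions may already require one. This stands to the extent that the loss is conditional. It does not remove the gap, because nothing supplied requires a new record or fixes its onset date, and a primary endpoint should not rest on unstated site practice.

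A reader might infer that every event opening in screening and worsening on drug is certain to drop out, or that worsening pre-existing conditions are lost too. The documents support neither. The first depends on how sites record the event. The second runs against 7.4.2.1 and 7.4.5, under which such a condition becomes an adverse event only when it worsens.

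It is also fair that these cases are not hidden. All adverse events, all AESIs, AESIs of Grade 3 or higher, and serious events are listed (SAP 15.1, 16.1, 16.2.2). AESIs and serious events are reported in an expedited manner, and an IDMC reviews the safety data. But listings do not enter the primary proportion or the comparison between arms.

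No between-arm bias has been shown. One rule applies to both arms under blinding, and the study is descriptive. The remaining risk is undercounted on-drug worsening, including any difference between arms in that worsening.

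**Conclusion.** The point holds in a limited form. An adverse event that starts between consent and first dose, is still open at first dose, and then worsens or becomes serious is excluded from the primary proportion and the adverse event tables if it is kept as one record with its screening onset. The supplied documents do not say whether it would be.

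The size is small. The range of 1 to 9 of 260 patients covers all adverse events and rests on a borrowed on-treatment rate, an assumed 2 to 4 weeks of screening, an unsourced 5% to 20% worsening share, and no new records being opened. If sites do open new records, the number is zero. For the primary endpoint, the rash calculation gives 0.06 to 0.46 patients, so probably fewer than one. It would be wrong to infer a material distortion of the primary result. The reason to act is that the definition can miscount severe or serious on-drug worsening, and putting it right is cheap.

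**What to change.** In SAP 16.1, add that an adverse event starting before first dose that increases in CTCAE grade, or becomes serious, on or after first dose is treatment-emergent from the date of worsening. Refer to this rule in 15.1 so that it governs the primary AESI endpoint.

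This needs a dated grade or seriousness change in the data. If the CRF holds only one severity per event, the SAP should state instead that each such worsening is a new record with onset at the date of worsening, and the CRF conventions should say the same. If those conventions already require this, one confirming sentence in the SAP is enough.

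Settle this before database lock and unblinding. SAP section 8 places the lock after the last patient's 4-month visit and bars unblinding until the SAP is approved, so the rule can be set blind. The cost is a sentence or two, a few site queries for events open at first dose, and slightly higher TEAE percentages. Patients would not be double counted, because SAP 16.1 counts a patient once per preferred term and the screening record would not itself be treatment-emergent.
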